# **GLOSSARY OF ABBREVIATIONS**

AE adverse event

APRI AST to platelet ratio index

AFP alfa fetoprotein

ALT alanine-aminotransferase AST aspartate-aminotransferase

ANCOVA analysis of covariance

BMI body mass index

BMQ beliefs medication questionnaire

CA competent authority

CD4 cluster of differentiation 4

CHC chronic hepatitis C
CI confidence interval

CNI calcineurin
CP core population

CPFSU core population with sufficient follow-up data

CT computer tomography

DAA direct-acting antiviral agent

DDI drug-drug interaction

EC ethics committee

EDC electronic data capture

eCRF electronic case report form

EMA European Medicines Agency

EoT end of treatment

EQ-5D-5L EuroQol 5 dimension 5 level

FDA Food and Drug Administration

FIB-4 Fibrosis-4 Score/Index

γ-GT gamma-glutamyltransferase HCC hepatocellular carcinoma

HCP health care provider

Hb hemoglobin

HbA1c hemoglobin A1c
HBV hepatitis B virus
HCV hepatitis C virus

# **GLOSSARY OF ABBREVIATIONS**

HDL high-density lipoprotein

HIV human immunodeficiency virus
HOMA homeostasis model assessment
HVPG hepatic venous pressure gradient

ICMJE International Committee of Medical Journal Editors

IEC/IRB independent ethics committee/- review board

IgA Immunoglobulin A
IgG Immunoglobulin G
IgM Immunoglobulin M

INN international non-proprietary name

INR international normalized ratio

LDL low-density lipoprotein

LLoD lower limit of detection

LLoQ lower limit of quantification

MAH Marketing Authorization Holder

MedDRA Medical Dictionary for Regulatory Activities

MLR multiple logistic regression
MRI magnetic resonance imaging

NCP non-core population

NS3/NS4A nonstructural protein 3/nonstructural protein 4A

NS5A nonstructural protein 5A NS5B nonstructural protein 5B

OATP organic anion-transporting polypeptide

OLT orthotopic liver transplant

paritaprevir/r paritaprevir/ritonavir

PCR polymerase chain reaction

pegIFN pegylated interferon

PRO patient reported outcome

PT preferred term

RBV ribavirin

RF rheumatoid factor RNA ribonucleic acid

SAE serious adverse event

# **GLOSSARY OF ABBREVIATIONS**

SAP statistical analysis plan SD standard deviation SDP study designated physician SNP single nucleotide polymorphism SOC system organ class SP safety population SVR sustained virological response SVR12 SVR at 12 weeks after EoT SVR24 SVR at 24 weeks after EoT TAI total activity impairment TP target population **TWP** total work productivity impairment VAS visual analogue scale WHO World Health Organization WPAI work productivity and activity impairment WPAI-GH WPAI as general health measure WPAI-SHP WPAI modified for specific health condition

## 1. INTRODUCTION

The interferon-free combination regimen of paritaprevir/r and ombitasvir with or without dasabuvir (ABBVIE REGIMEN) ± ribavirin (RBV) for the treatment of chronic hepatitis C (CHC) has been shown to be safe and effective in randomized controlled clinical trials with strict inclusion and exclusion criteria under well controlled conditions.

The rationale for this observational study is to determine how the efficacy and safety of the ABBVIE REGIMEN as demonstrated in pivotal trials translates into real world everyday clinical settings, which means evaluating its effectiveness. Whereas efficacy can be defined as a measure of the capacity of a treatment to produce the desired effect in a controlled environment, such as in a randomized controlled trial, effectiveness is the extent to which a drug achieves its intended effect in the usual clinical setting. Effectiveness trials typically have limited exclusion criteria and will involve the broader patient populations in routine clinical practice, treated per local label, which might include patients with heterogeneous compliance patterns and patients with significant comorbid conditions and could be used to model and disseminate best practices. Effectiveness research allows for external patient-, provider-, and system-level factors and can therefore be more relevant for health-care decisions by both providers in practice and policy-makers.

This observational study is the first effectiveness research examining the ABBVIE REGIMEN ± RBV, used according to local label, under real world conditions in Poland in a clinical practice patient population.

During the last decade, when dual therapy with pegylated interferon (pegIFN) plus RBV was standard of care for the treatment of CHC, the discovery of predictive factors for virological response and the subsequent development of treatment algorithms marked a milestone in patient care for CHC. As a consequence, treatment could be effectively targeted to patients most likely to respond. Interestingly, many of the now well established predictors of response to pegIFN/RBV and first generation direct acting antivirals (DAAs) in combination with pegIFN/RBV were not predictive of outcome in the development trials of the ABBVIE REGIMEN ± RBV. This observational study may play an important part in bridging the data gaps. It may help identify predictive factors of response that are important in real world treatment settings and thus, could assist in further optimizing treatment with the interferon-free ABBVIE REGIMEN ± RBV in the future.

The label of the ABBVIE REGIMEN ± RBV will vary according to hepatitis C virus (HCV) genotype/subtype and stage of liver disease. It is therefore relevant to understand the pattern of use and outcome in daily clinical practice. In addition, this study will provide data on the impact of adherence on treatment outcomes in everyday settings, which may help treating physicians to improve the management of patients under their care.

The main aim of this observational study is to provide evidence of the effectiveness of the ABBVIE REGIMEN ± RBV in a real world setting across clinical practice patient populations.

#### 2. STUDY OBJECTIVES

The objectives of this study are:

#### Primary objective:

 To describe in routine clinical practice the effectiveness of the interferon-free ABBVIE REGIMEN ± RBV in patients with CHC as evidenced by sustained virological response at 12 weeks after end of treatment (SVR12)

#### Secondary objectives:

- 2. To provide real world evidence for predictive factors of virological response
- 3. To describe the pattern of real world use of the ABBVIE REGIMEN ± RBV with respect to different patient and treatment characteristics
- 4. To evaluate the influence of adherence on treatment outcome in routine clinical practice
- 5. To collect information on co-morbidities and concomitant medication in the Polish population
- 6. To describe the tolerability of the ABBVIE REGIMEN ± RBV
- 7. To document the effect of the ABBVIE REGIMEN  $\pm$  RBV on PROs and work productivity in the Polish population

# 3. STUDY DESIGN

# 3.1 Overview of Study Design and Dosing Regimen

This is a prospective, multi-center observational study in adult patients chronically infected with HCV receiving the interferon-free ABBVIE REGIMEN ± RBV.

University centers and outpatient clinics qualified by training and experience in the management of patients with CHC participate in this study.

The prescription of a treatment regimen is at the discretion of the physician in accordance with local clinical practice and label, is made independently from this observational study and precedes the decision to offer the patient the opportunity to participate in this study.

After written patient authorization has been obtained, patient data including demographic data, HCV disease characteristics, co-morbidities, co-medication, treatment details, and laboratory assessments as recorded in the patient's medical records (source documentation) are documented in the electronic case report form (eCRF). Patients are observed for the duration of the ABBVIE REGIMEN therapy and for up to 24 weeks after treatment completion.

[figure not shown]
The observational period for patients receiving 12 weeks of ABBVIE REGIMEN is max. 36 weeks (12 weeks treatment and 24 weeks post-treatment observation) and for patients receiving 24 weeks of ABBVIE REGIMEN the observational period is max. 48 weeks (24 weeks treatment and 24 weeks post-treatment observation).

Follow-up visits, treatment, procedures and diagnostic methods follow physicians' routine clinical practice. The observational study period entails the following data collection schemes, data documented are those closest to the time windows as indicated in Figure 1:

- 12-week treatment regimen: four visits plus two interim data collection windows
- 24-week treatment regimen: four visits plus three interim data collection windows

This schedule is based on the anticipated regular follow-up for patients undergoing treatment for CHC.

Figure 1 - Study Flowchart

# 3.2 Sample Size Calculation

In phase III studies investigating the interferon-free ABBVIE REGIMEN  $\pm$  RBV, SVR12 rates of at least 90% were observed, even in difficult-to-treat CHC patients (e.g. cirrhotic G1a treatment experienced patients). It is expected that 400 patients treated with the ABBVIE REGIMEN  $\pm$  RBV can be included into this observational study during the planned inclusion period of 6 months, and that about 90 to 95% of the patients enrolled will be evaluable in the core population (see Section 4.2.1 for the definition of the core population). As shown in Table 1, if the SVR12 rate is at least 90% and there are 360-380 evaluable patients, then the width of the 95% confidence interval (CI) will not be wider than 6.5%. If the SVR12 rate is at least 95% and there are 360-380 evaluable patients, then the 95% CI will have a width of less than 5%. With at least 340 evaluable patients the width is still less than 5%, if the SVR12 rate is at least 95%.

Number of	SVR12 rates	95% Confidence Interval*			
patients		Lower Limit	Upper Limit	Width	
340	90%	86.3	93.0	6.7%	
340	95%	92.1	97.1	4.9%	
360	90%	86.4	92.9	6.5%	
360	95%	92.2	97.0	4.8%	
380	90%	86.5	92.8	6.3%	
380	95%	92.3	97.0	4.7%	

Table 1 Width of 95% Confidence Interval for SVR12

## 4. STATISTICAL CONSIDERATIONS AND ANALYTICAL PLAN

# 4.1 Primary and Secondary Parameters

## 4.1.1 Primary Effectiveness Parameter

The percentage of patients achieving SVR12 (HCV RNA <50 IU/mL 12 weeks [i.e. 70 to 126 days] after the last actual dose of the ABBVIE REGIMEN).

Please note, in the study protocol no upper boundary for the time window was specified. The upper boundary of 126 days was introduced to achieve consistency with other studies investigating the ABBVIE REGIMEN  $\pm$  ribavirin (RBV) for the treatment of CHC. For the handling of missing values see section 4.2.3.

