No data will be imputed for any effectiveness or safety analyses except for the analyses of the HCV RNA endpoints. When there is no HCV RNA value in a visit time window post-baseline, but prior to EoT, the closest values before and after the window, regardless of the value chosen for the subsequent and preceding window, will be used for the flanking imputation described below. If a patient has a missing HCV RNA value at a post-baseline visit prior to EoT but has undetectable HCV RNA (with LLoD ≤ 50 IU/mL) or unquantifiable, but detectable HCV RNA levels (with LLoQ ≤ 50 IU/mL) at both the preceding and succeeding measurements, the HCV RNA level will be considered undetectable or unquantifiable, respectively, at this visit for this patient. In addition, if a patient has an unquantifiable HCV RNA level at the preceding measurement and an undetectable HCV RNA level at the succeeding measurement, or vice versa, the HCV RNA level will be imputed as unquantifiable at this visit for this patient. For virological response at EoT a corresponding backward imputation approach will be applied. This means if HCV RNA is missing at EoT, then unquantifiable or undetectable will be assumed for EoT, if the succeeding HCV RNA value is undetectable or unquantifiable. For SVR12 the single last available HCV RNA measurement ≥ 70 days post-treatment will be used. Subsequent to this flanking and backward imputation, if the HCV RNA value remains missing at a specific time point, then the patients will be considered as virological failure at this time point (i.e. not undetectable or unquantifiable).

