9.7.3.1 Primary Effectiveness Endpoint

The percentage of patients achieving SVR12 (single last HCV RNA < 50 IU/mL 12 weeks [i.e. at least 70 days] after the last actual dose of the ABBVIE REGIMEN) is the primary effectiveness endpoint.

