# 4.2.3 Handling of missing data

No data will be imputed for any effectiveness or safety analyses except for the analyses of the HCV RNA endpoints and certain PRO endpoints. The discussion of missing data imputation for the PRO endpoints is included in section 4.2.7.2.3.

HCV RNA values will be selected for an RVR, EOTR and SVR analysis based on visit windows as defined in Table 3. When there is no HCV RNA value in a visit window based on defined visit windows, the closest values before and after the window, regardless of the value chosen for the subsequent and preceding window, will be used for the flanking imputation described below. For analysis of RVR, EOT and SVR, if a subject has a missing HCV RNA value at a post-Day 1 visit but with undetectable or unquantifiable (≤50 IU/mL) HCV RNA levels at both the preceding value and succeeding value, the HCV RNA level will be considered undetectable or unquantifiable,

respectively, at this visit for this subject. In addition, if a subject has an unquantifiable HCV RNA level at the preceding value and an undetectable HCV RNA level at the succeeding value, or vice versa, the HCV RNA level will be imputed as unquantifiable at this visit for this subject.

For analyses of RVR, subjects still missing a value for the visit after flanking imputation will be imputed as a failure. For EoTR and SVR analysis, if there is no value in the appropriate window after flanking imputation but there is an HCV RNA value after the window, then it will be imputed into the EoTR or SVR window respectively. Subsequent to this flanking imputation, if a subject is missing a value for the visit window associated with the analysis, the subject will be imputed as a visit failure (i.e., not undetectable or unquantifiable).

If a subject starts another treatment for HCV, then all HCV RNA values for this subject measured on or after the start date of the new HCV treatment will be excluded from analyses. The subject will be considered a failure for summaries of viral response at all time points after the start of the new HCV treatment.

Due to the non-interventional nature of this study several different methods for determination of the HCV RNA value can be applied. For the purpose of the statistical analysis, a HCV RNA measurement is considered ≤50 IU/mL.

- if a PCR test was used

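### The SAP limits SVR12 to days 70–126 without carrying over the protocol's last-value rule, and its text plans no analysis under the protocol's own primary definition

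*SAP*

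**What the plan says.** Protocol 9.7.3.1 defines the primary endpoint as the percentage of patients with "single last HCV RNA < 50 IU/mL 12 weeks [i.e. at least 70 days] after the last actual dose of the ABBVIE REGIMEN". Protocol 9.7.1 gives the matching selection rule: "For SVR12 the single last available HCV RNA measurement ≥ 70 days post-treatment will be used". Neither sets a latest day, and Protocol 9.2.2 plans observation to 24 weeks post-treatment, so values well beyond week 12 are expected.

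SAP 4.1.1 defines the same endpoint as "HCV RNA <50 IU/mL 12 weeks [i.e. 70 to 126 days] after the last actual dose of the ABBVIE REGIMEN". It declares the departure ("Please note, in the study protocol no upper boundary for the time window was specified") and gives a reason ("The upper boundary of 126 days was introduced to achieve consistency with other studies investigating the ABBVIE REGIMEN"). SAP Table 3 assigns days 127–210 to SVR24. On which value is used, SAP 4.2.3 says: "HCV RNA values will be selected for an RVR, EOTR and SVR analysis based on visit windows as defined in Table 3". It states no order of precedence when several values fall in one window.

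If the window is empty, SAP 4.2.3 first applies flanking imputation from the nearest values on either side. If that does not fill the gap, it carries a later value back into the window. It also discards all values from the start of any new HCV treatment. The sensitivity analysis in SAP 4.2.7.1 repeats the primary analysis in the CPSFU. That changes the population, not the endpoint.

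**The concern.** The two documents can score the same patient differently on the primary endpoint. Under the protocol, viraemia documented at week 24 overrides a negative week-12 value. Under the SAP it does not, because the later value belongs to another window. The SAP note covers the upper bound but is silent on which value counts inside the window, so a negative on day 75 followed by a positive on day 120 is left to the programmer.

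The study exists to estimate this one rate. A reader who compares the reported SVR12 with the protocol definition cannot tell from the planned analyses whether the redefinition moved it.

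**Working it through.** **Inputs.** Evaluable patients: 360–380 (Protocol 9.5, SAP 3.2). Planning SVR12 rates: 90% and 95% (Protocol Table 3, SAP Table 1). Scoring rules: Protocol 9.7.1 and 9.7.3.1; SAP 4.1.1, Table 3 and 4.2.3. Late-relapse rate: not given in either document, so assumed.

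**Step 1: the plan's precision.** Clopper-Pearson limits are the beta quantiles B(0.025; x, n−x+1) and B(0.975; x+1, n−x). At a 95% rate the width is 4.80 points for n = 360 and 4.66 for n = 380; at 90% it is 6.47 and 6.29. These match the stated 4.8, 4.7, 6.5 and 6.3. The half-widths at 95% are 4.80/2 = 2.40 and 4.66/2 = 2.33 points. SAP 4.2.7.1 uses Wilson intervals instead; those widths are 4.58 and 4.45 points, so the comparison below hardly changes.

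**Step 2: the two rules applied to example histories** (days after last dose, no new HCV treatment, EoT value below 50 IU/mL).

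| HCV RNA history | Protocol | SAP |
|---|---|---|
| <50 on day 84, ≥50 on day 168 | failure | responder |
| <50 on days 40 and 140, ≥50 on day 190; window empty | failure | responder (flanking) |
| ≥50 on day 84, <50 on day 168 | responder | failure |
| window empty, ≥50 on day 168 | failure | failure (carried back) |
| <50 on day 84, nothing later | responder | responder |
| <50 on days 84 and 168 | responder | responder |
| <50 on day 75, ≥50 on day 120 | failure | not stated |

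The upward switch therefore needs a value below 50 IU/mL in days 70–126, measured or imputed there by flanking, and a value at or above 50 IU/mL later. The downward switch needs viraemia in the window and a negative later value without retreatment.

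**Step 3: weight of one patient.** 1/380 = 0.26 points; 1/360 = 0.28 points.

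**Step 4: illustrative totals.** Patients reclassified upward = n × 0.95 × r, where r is the assumed share of SAP responders with documented viraemia after day 126.

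| r (assumed) | n = 360 | n = 380 | Shift = 95% × r |
|---|---|---|---|
| 0.5% | 1.7 | 1.8 | about 0.5 points |
| 1% | 3.4 | 3.6 | 0.95 points |
| 2% | 6.8 | 7.2 | 1.9 points |

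In whole patients at n = 360, a SAP rate of 342/360 = 95.0% (Clopper-Pearson CI 92.2–97.0) becomes under the protocol rule:
- 341/360 = 94.7% (91.9–96.8) with one net reclassification;
- 338/360 = 93.9% (90.9–96.1) with four;
- 335/360 = 93.1% (89.9–95.5) with seven.

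**Step 5: whether another planned output gives the protocol figure.** Relapse24 (SAP 4.2.7.2.1) counts relapse in the SVR24 window, but only among CP patients with EoT response who completed treatment. SVR24 is reported in the CPSFU for SVR24, which leaves out patients whose last value was a response and who have no value after day 126 for reasons unrelated to safety or effectiveness (SAP 4.2.1). Both show late relapses. Neither has the denominator or the scoring rule of the protocol's SVR12 in the CP.

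**The case against.** The strongest reply is that this is a declared refinement within delegated scope. SAP 4.1.1 names the change and its reason, Protocol 9.7.1 leaves the HCV RNA time windows to the SAP, and the protocol schedules separate SVR12 and SVR24 visits. An upper bound stops a week-24 value from deciding an endpoint named for week 12. All of that stands, and it is why the window need not be withdrawn. It does not cover the choice of value, which the protocol fixes itself and the SAP does not address.

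A reader might infer more than the documents support:

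- **That the last-value rule was revoked.** The SAP is silent on it; nothing stops it being applied within the window. The gap is a missing statement.
- **That the change can only raise the rate.** The reverse history in step 2 lowers it. Protocol 9.9 notes that centres use different assays, including in-house ones, which may change between visits, so discordant results could arise either way. The protocol also has no retreatment exclusion: as written, a patient who relapsed, was retreated and then tested negative would count as a responder there, while the SAP discards the post-retreatment value.
- **That every late relapse is lost or turned into a response.** Relapse24 and SVR24 retain late relapses, and with an empty window and a positive next value the patient fails under both rules.
- **That no output can contain the protocol figure.** The table shells (SAP Part II) are not among the documents reviewed. What can be said is that the SAP text plans none.

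The size also rests on an assumed rate, and the study is descriptive, with no SVR12 threshold to cross.

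**Conclusion.** The definitions differ, and that follows from the text alone. The net direction is mainly upward, as a matter of judgement: a negative week-12 value followed by viraemia is an ordinary late relapse, whereas the reverse needs viraemia that clears without retreatment, or an assay discrepancy. The size is 0.26–0.28 points per patient. The total of about 0.5–1.9 points is illustrative only; it assumes a 95% rate, 0.5–2% late viraemia among responders and no offsetting downward switches. Even the top of that range lies inside the planned CI half-width, and the planned sample size is unaffected. This is a low-cost improvement to the reporting of the primary endpoint, not a finding that the estimate is invalid.

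**What to change.** Keep the 70–126 day window and make two changes:

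1. In SAP 4.1.1 and 4.2.3, state that when several values fall in the SVR12 window, the last one is used, as the protocol's selection rule implies.
2. In the CP response table (tvr_<c>_gc_cp), add a sensitivity row with SVR12 under the protocol rule: the single last HCV RNA value at day 70 or later. Apply the SAP 4.2.3 retreatment exclusion to both rows, so that they differ only in the SVR12 rule. Give the 95% CI and the number of patients whose status differs, separately for each direction.

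The cost is one sentence and one table row, with no new data. The protocol-defined figure may be slightly less favourable. If nobody switches, the row shows that the redefinition made no difference.

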# 4.2 Statistical and Analytical Methods

# 4.2.1 Analysis Populations and Analysis Groups

# Population of Patients Enrolled [EP]

The population of patients enrolled comprises all patients who voluntarily sign and date a patient authorization to use prior to inclusion into the study and data were captured in the eCRF.

#### **Target Population [TP]**

Patients will be included if the following applies:

- Age at least 18 years
- Confirmed CHC with genotype 1 and/or 4 only, receiving combination therapy with the interferon-free ABBVIE REGIMEN ± RBV. The prescribed ABBVIE REGIMEN needs to be known.
- Have voluntarily signed and dated a patient authorization to use prior to inclusion into the study
- Must not be participating or intending to participate in a concurrent interventional therapeutic trial

